- S/P cardiac arrest
- Cardiogenic Shock
- Acute myocardial infarct with complications
- Cardiac tamponade
- Acute congestive heart failure
- Acute or imminent respiratory failure
- Hemodynamic instability
- Diabetic ketoacidosis complicated by hemodynamic instability, altered mental status, respiratory insufficiency, or severe acidosis
- Other conditions requiring specialized equipment and/or staff competencies only available in the ICU

3. Non-ICU hospitalization, requiring supplemental oxygen

Subject met either of the 2 following criteria:

- Non-ICU hospitalized on the day of assessment (including readmittance), not ready for discharge during the whole day of assessment, as judged by the investigator and supplemental oxygen is required by the subject
- In the ICU but there is no medical reason to be in the ICU during the day of assessment, and supplemental oxygen is required by the subject

Requiring supplemental oxygen is defined by:

- Receiving supplemental oxygen through a face mask or nasal cannula and not being able to sustain a blood oxygen saturation of $\geq 94\%$ when breathing room air for 15 minutes at any time on the day of assessment.
- If supplemental oxygen was provided chronically pre-influenza infection (based on medical history), that amount of supplemental oxygen is exceeded to prevent hypoxia, tachypnea or dyspnea at some point on the day of assessment.
- Not receiving supplemental oxygen and either:
 - Having a blood oxygen saturation of $< 94\%$ when breathing room air for 15 minutes at any measurement on the day of assessment, or
 - In case of known pre-influenza $SpO_2 < 94\%$ (eg, due to COPD), the current blood oxygen saturation on room air is lower than pre-influenza infection levels by at least 3%.

2. Non-ICU hospitalization, not requiring supplemental oxygen

Subject met either of the 2 following criteria:

- Non-ICU hospitalized on the day of assessment (including readmittance) and not ready for discharge during the whole day of assessment, as judged by the investigator
- In the ICU but there is no medical reason to be in the ICU during the day of assessment

1. Not hospitalized

Any of the following:

- Discharged from the hospital before the day of assessment
- Hospitalized at the day of assessment but ready for discharge on both the day of assessment and the day prior, as judged by the investigator (eg, in case of lack of bed availability in a skilled nursing facility, lack of social support at home).

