Blood oxygen saturation will be measured using a standard pulse oximeter. If possible, the same type of probe should be used for all subjects enrolled at the site while they are hospitalized. The SpO₂ should be measured either in a sitting or supine position after 5 minutes of rest in a quiet environment. Subjects should be encouraged to sit still during the measurements. Pulse oximetry measurements using finger, toe, earlobe or frontal sensors are considered acceptable. If using the digits, nail polish should be removed, and warmth and capillary refill should be assessed, since adequate arterial pulse strength is necessary for obtaining accurate SpO₂ measurements. The sensor should not be placed on sites distal to indwelling arterial catheters, blood pressure cuffs, or venous engorgement (eg, arteriovenous fistulas, blood transfusions). If supplemental oxygen is provided to the subject by either nasal cannula, face mask, or a reservoir system, remove supplemental oxygen while the subject is appropriately monitored. Wait for either 5 minutes to elapse with oxygen saturation maintained at or above 94%, or until saturation declines to less than 94%. (For subjects with known pre-influenza illness SpO₂ levels of <94%, the pre-influenza SpO₂ level should be used as target level instead of 94%). Document those findings, then either return to previous level of supplemental oxygen therapy or discontinue therapy. For subjects receiving invasive or non-invasive mechanical ventilation, peripheral oxygen saturation should be measured with the ventilatory support in place, and it should be recorded that the measurement was with supplemental oxygen.

Blood pressure, pulse rate, and respiratory rate measurements should be preceded by at least 5 minutes of rest in the supine position in a quiet setting without distractions (eg, television, cell phones). These measurements will be assessed with a completely automated device. Manual techniques will be used only if an automated device is not available.

The level of consciousness will be measured according to the ACVPU scale (alert, new confusion, voice, pain, unresponsive).¹⁰

- Alert: The subject is fully awake. This subject will have spontaneously opening of the eyes, will respond to voice, and will have motor function.

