	
Within 1 timepoint the assessments of the different parameters are taken together for evaluating the clinical response and the time of the last record within that time point is used. Unscheduled assessments are not taken into account. When multiple assessments for 1 parameter occur within one timepoint then only the last is used for that parameter.
 
Table 4: Resolution Criteria for Vital Signs
 
  
 Assessment	Resolution Criterion	
   
 Temperature	Oral temperature ≤ 37.0 °C (without the use of antipyretics within 8 hours)*¹	
 
 Oxygen saturation	a) $\geq 94\%$ on room air without supplemental oxygen*² b) In case pre-influenza infection oxygen saturation $< 94\%$*³: Return to pre-influenza oxygen saturation*⁴	
 
 Respiration rate	≤ 24/min or return to pre-influenza infection oxygen requirement in patients with chronic oxygen use*^{4,5}	
 
 Heart rate	≤ 100/min	
 
 Systolic blood pressure	≥ 90 mmHg (without inotropic support given within 2 hours of assessment) *⁶	
  
 
*¹Based on the Vital Signs form, question “Were there any antipyretic medications given within 8 hours before temperature measurement?”
 
*²Based on the oxygen saturation level measured on room air and “YES” on the question ‘Is the patient able to sustain a blood oxygen saturation $\geq 94\%$ when breathing room air for 15 min at any time on the day of assessment?’ on the vital signs form.
 
*³ If pre-influenza oxygen saturation level is below 94% and measured on room air
 
*⁴Return to pre-influenza infection oxygen requirement is based on the oxygen supplementation form: “Has supplemental oxygen administration returned to that level provided prior to the current respiratory infection?”
 
*⁵Chronic oxygen use is based on the question “Does the subject require chronic oxygen”
 
*⁶ Inotropic support given within 2 hours of assessment as recorded in the vital signs form.
	Assessment	Resolution Criterion	Temperature	Oral temperature ≤ 37.0 °C (without the use of antipyretics within 8 hours)* ¹	Oxygen saturation	a) $\geq 94\%$ on room air without supplemental oxygen* ² b) In case pre-influenza infection oxygen saturation $< 94\%$ * ³ : Return to pre-influenza oxygen saturation* ⁴	Respiration rate	≤ 24 /min or return to pre-influenza infection oxygen requirement in patients with chronic oxygen use* ^{4,5}	Heart rate	≤ 100 /min	Systolic blood pressure	≥ 90 mmHg (without inotropic support given within 2 hours of assessment) * ⁶

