ATTACHMENT 6. : HRS DERIVATION

The HRS categories should be evaluated from 6 to 1. First check if the subject falls in category 6 (has the subject died?) if not then we evaluate category 5, if not 5 then evaluate category 4 and so on.

The HRS is evaluated at baseline and per day, relative to the first study drug intake.

The baseline HRS is covering the full baseline/screening/day 1 visit which can occur on 2 days.

Timing of first study drug intake is not taken into account.

Note:

- VSOXYSAT is assessed 3 times per day (or per baseline visit). In case one of the assessments says 'N' then the final result for that day (or baseline visit) is 'N', else if one of the assessments is 'NA' then the final result is 'NA' else if one of the assessments is missing then final result is missing.

So a combination of 'Y', "", "N" → result ='N'

'Y', "", "NA" → result ='NA'

'Y','Y','' → result =''

'Y','Y','Y' → result ='Y'

On the baseline visit, on days at or after HO end date or on the day of discontinuation it might be that less than 3 assessments are done. Therefore, take only the records into account from the dataset on those days as planned. The same rules above apply to derive the final result per day when more than 1 assessment is collected.

- In case the subject withdrew from the study, the HRS will be set to missing from the next day onwards.
- In case of chronic oxygen use and multiple CMARTN values on a day we consider the worst value: In case one of the values is 'N' then final result for that day (or baseline visit) is 'N', else if one of the assessments is missing then final result is missing.
- The list of types of supplemental oxygen and invasive mechanical ventilation can be extended depending on the medical review (see DPS part 2 or Excel sheet of the medical review)
- The list of hospitalization terms (i.e.: ICU or WARD) can be extended depending on the medical review (see DPS part 2 or Excel sheet of the medical review).
- If the Subjects has no HO data, the subject is considered to be in the hospital during the trial. All other aspect of the HRS will be evaluated according to the derivation below.
- In case the readiness for discharge (RDISHOSP) is assessed more than once per day (baseline visit) we consider the worst value: in case one of the values is 'N' then the final result of that day (or baseline visit) is 'N'

Some clarification is required for following categories:

6. Death

When DM.DTHDTC<=(date of assessment)

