5. Requiring invasive mechanical ventilation;

When CMSTDTC<=(date of assessment) <=CMENDTC where CMADMTP="INVASIVE MECHANICAL VENTILATION"

And CMADMDS in ('Through Endotracheal tube' 'Through Tracheostomy tube' or 'Through ECMO')

4. Admitted to the ICU;

From the HO data set:

hostdy <=(day of assessment)<=hoendy
hoterm = 'ICU'

From the SS data set:

SSTESTCD= 'REQICU' and SSSTRESC='Y'
Or SSTESTCD= 'REASICU' and SSSTRESC='Y'
Or both REQICU and REASICU is missing and NOT (RDISHOSP = 'Y' on the day of assessment and RDISHOSP = 'Y' on the day (baseline visit) before)

OR

From the HO data set:

hostdy <=(day of assessment)<=hoendy
hoterm = 'WARD'

From the SS data set:

SSTESTCD='REASICU' and SSSTRESC='Y'
OR
SSTESTCD='REQICU' and SSSTRESC='Y'

3. Non-ICU hospitalization, requiring supplemental oxygen

Non-ICU hospitalization:

hostdy <=(day of assessment)<=hoendy
hoterm = 'Hospital inpatient Department (WARD)'
NOT (RDISHOSP='Y' on the day of assessment and RDISHOSP='Y' on day(baseline visit) before)

OR

hostdy <=(day of assessment)<=hoendy
hoterm = 'ICU'
NOT (RDISHOSP='Y' on the day of assessment and RDISHOSP='Y' on day(baseline visit) before)

OR

(day of assessment)=hoendy+1
RDISHOSP='N' on day(baseline visit) before

OR

In case re-hospitalization occurred (there is a day between the HOENDY of the previous record and HOSTDY of the next record)
(day of assessment) =HOSTDY (of the re-hospitalization)
NOT (RDISHOSP='Y' on the day of assessment and RDISHOSP='Y' on day(baseline visit) before)

AND

Requiring supplemental oxygen:

'Receiving supplemental oxygen through a face mask or nasal cannula and not being able to sustain a blood oxygen saturation of $\geq 94\%$ when breathing room air for 15 minutes at any time on the day of assessment.'

FAOBJ=CHRONIC OXYGEN USE and FAORRES='N'

CMADMTP in ("Non-Invasive Mechanical Ventilation", "Nasal Cannula", "Venturi Mask", "Simple Face Mask", "Nonrebreathing Face Mask with Reservoir and One-Way Valve".)

CMTRT=SUPPLEMENTAL OXYGEN and CMSTDTC <= date of assessment <= CMENDTC

VSOXYSAT in ('N' 'NA') at any time during the day of assessment (OR is missing)

OR

'If supplemental oxygen was provided chronically pre-influenza infection (based on medical history), that amount of supplemental oxygen is exceeded to prevent hypoxia, tachypnea or dyspnea at some point on the day of assessment.'

FAOBJ=CHRONIC OXYGEN USE and FAORRES='Y'

CMARTN = 'N'

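### SAP Attachment 6 contradicts itself on a missing oxygen answer (Cases 7 and 10), so the same Day 6 data can be programmed as category 2 or 3; the 5-minute and 15-minute room-air checks also need aligning

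*Protocol*

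**What the plan says.** **Derivation (SAP Attachment 6).** The form variable `VSOXYSAT` records whether the subject can hold at least 94% on room air. It is collected three times a day and rolled up to one daily value. N takes precedence. Failing that, if "one of the assessments is 'NA' then the final result is 'NA". Failing that, any blank makes the day missing, and only an all-Y day is Y. For a subject receiving oxygen without chronic use, oxygen counts as required when "VSOXYSAT in ('N' 'NA') at any time during the day of assessment (OR is missing". For a chronic user receiving oxygen, the rule needs `CMARTN` = N, meaning that oxygen has not returned to the pre-influenza level. Worked cases follow.

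**Definition (Protocol 9.2.1.1; SAP 5.2.1).** Category 3 rests on whether the subject can hold at least 94% "when breathing room air for 15 minutes at any time on the day of assessment". It also takes in subjects who are "In the ICU but there is no medical reason to be in the ICU during the day of assessment, and supplemental oxygen is required". The vital signs form question, cited in footnote 2 of SAP Table 4, uses the same period: "when breathing room air for 15 min at any time on the day of assessment".

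**Measurement (Protocol 9.6.4).** With oxygen removed, sites are told: "Wait for either 5 minutes to elapse with oxygen saturation maintained at or above 94%, or until saturation declines to less than 94" (per cent). Then: "Document those findings, then either return to previous level of supplemental oxygen therapy or discontinue therapy". Ventilated subjects have no removal step: "For subjects receiving invasive or non-invasive mechanical ventilation, peripheral oxygen saturation should be measured with the ventilatory support in place".

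**The concern.** The Day 6 hospital recovery scale is the primary endpoint, and categories 2 and 3 together hold 55% of the planned placebo distribution (30% + 25%). The split between them depends on the oxygen rule. If the rule text and its worked cases disagree, two programmers working correctly from the same SAP can produce different primary data sets, and a validation check against the cases would fail code that follows the rule.

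The duration mismatch arises earlier, at the bedside. A subject who holds at least 94% for 5 minutes and is put back on oxygen need not have been observed for minutes 5 to 15, which the form asks about. Sites may answer differently. The same form question also feeds the saturation criterion for time to clinical response and time to respiratory response (SAP Table 4).

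**Working it through.** **1. Attachment 6: rule against cases** (all subjects receiving oxygen)

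| Source | Chronic use | `VSOXYSAT` | `CMARTN` | Reading <94% | Oxygen required? |
|---|---|---|---|---|---|
| Rule text | No | missing | not used | not used | YES |
| Case 1 | No | N, missing or NA | not used | not used | YES |
| Case 7 | No | missing | not used | yes | **NO** |
| Rule text | Yes | not used | must be N | not used | NO if missing |
| Case 10 | Yes | missing | missing | not used | **YES** |

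Case 7 falls inside Case 1, because its only extra input is one that Case 1 says is not used. That input also points the other way clinically: Case 4, a subject off oxygen with `VSOXYSAT` missing or NA and a reading below 94%, is YES. Case 7's column reads coherently from top to bottom, so a table damaged in extraction is an unlikely explanation.

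The disputed branch is easy to reach. Under the roll-up, answers of Y, Y and blank give a missing day. If that day also carries a reading below 94%, the rule and Case 1 give category 3, while Case 7 sends the subject on to category 2.

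**2. Duration: tracing a 5-minute pass.** The mismatch affects subjects on the ward, or in the ICU without medical need, who receive non-ventilatory oxygen, are not chronic users, hold at least 94% for 5 minutes and go back on oxygen. Under the rule text:

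- all answers Y: category 2
- any N, any NA, or a missing day: category 3

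It does not affect subjects who fall below 94% (answer N), who stop oxygen (room air continues and can be observed for 15 minutes), who use oxygen chronically (the rule uses `CMARTN`), or who are ventilated.

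**3. Size.** Inputs from Protocol 11.3 and 11.4: placebo 30/30/25/5/5/5%, common odds ratio about 0.62 (38% reduction), N = 600 at 1:1, two-sided 5%. Proportional odds give pimodivir 40.9/29.9/19.4/3.4/3.3/3.2%.

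- Plan's figure: N = 12(1.960 + 1.282)² / [0.478² × (1 − Σp̄³)], with Σp̄³ = 0.0825, gives 601.4 against 600 stated. The sample size reproduces.
- Power at 600: V = (600/12)(1 − 0.0825) = 45.9; Φ(0.478 × √45.9 − 1.96) = 89.9%.

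The documents give no affected share, so 5/10/20% are assumptions. A random share is moved equally in both arms and the proportional odds model refitted:

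| Misplaced | Power at 5/10/20% | Odds ratio |
|---|---|---|
| 3 recorded as 2 | 89.65/89.38/88.85% | 0.621/0.622/0.624 |
| 2 recorded as 3 | 89.55/89.17/88.48% | 0.622/0.624/0.628 |

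At 20%, the 2-to-3 move involves 18 of 300 placebo subjects (0.20 × 0.30 × 300) and 17.9 of 300 on pimodivir. The largest loss is 89.94 − 88.48 = 1.46 points. If the category boundary merely shifts, with the odds ratio kept at 0.62, the loss is at most 0.28 points.

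Near-total loss of the boundary: merging categories 2 and 3 gives V = 40.7 and power 86.2%. Moving a random 80–90% of category 2 into 3 gives 86.1%. So 86.2% is not a strict floor, and about 86% is the fair description. Covariates and the interim combination test are ignored.

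**The case against.** The strongest objection is to the duration point. A reader might infer that the plan leaves the Day 6 score open for subjects who pass at 5 minutes. The documents do not support that. Once the form is answered, the Attachment 6 rule text is deterministic: N, NA and missing all give category 3, and only an all-Y day gives 2. That is a cautious default for someone whose clinician resumed oxygen. Score 2 arises only if a site answers Y to a question that states 15 minutes. Protocol 9.6.4 is also a general measurement procedure. It does not forbid watching for longer, and the definition allows the observation at any time of day. The eCRF completion guidelines mentioned in Protocol 17.6 were not available and may already tell sites how to answer and when to use NA. All of this stands, and it reduces the duration point to harmonisation.

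It does not reach the Attachment 6 conflict. The cases illustrate explicit rule text, and one could say the text governs, but the SAP does not say so. Completion guidelines govern data entry and cannot settle a contradiction inside the derivation. The conflict does need a missing answer on the day, and for Case 7 also a reading below 94%. No missing-data rate is given, so its frequency is unknown.

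**Conclusion.** Attachment 6 is wrong as written: Case 7 contradicts the category 3 rule and Case 1, and Case 10 contradicts the chronic-use rule. The 5-minute and 15-minute texts should agree, but that is secondary.

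The point is minor. The expected effect is noise and poor reproducibility at the 2/3 boundary: at most about 1.5 points of power at an assumed 20% share, and about 4 points, to about 86%, if the boundary were almost entirely lost. This assumes the planning distribution, an odds ratio of 0.62 and equal misplacement in both arms.

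A reader might infer bias between arms, an inflated type I error or a wrong sample size. The documents support none of these. Under blinding both faults should act alike in the two arms, and the sample size reproduces. Planned analyses also show whether a result depends on this boundary: four of the five dichotomizations do not use it (SAP 5.2.3), nor does not being hospitalized on Day 6, and the fundamental scale does not use the room-air test (SAP 5.3.1.1). They do not settle the primary score itself.

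**What to change.** 1. In SAP Attachment 6, change Case 7 to YES.
2. Add 'or missing' to the `CMARTN` = N condition, so that the chronic-use rule matches Case 10 and a missing answer is treated the same way in both branches. The alternative is to change Case 10 to NO.
3. Unless the eCRF guidelines already settle the answer, use one duration in Protocol 9.6.4 and 9.2.1.1, SAP 5.2.1, Table 4 footnote 2 and the form question. One option is to extend the 9.6.4 check to 15 minutes and keep the stop at a fall below 94%. The sponsor should decide which duration is clinically right.
4. State that a completed off-oxygen test is answered Y or N, and reserve NA for subjects with no removal step.

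Items 1 and 2 are edits to the SAP and its programming specification. Items 3 and 4 need wording changes and a site memo, with no extra visits. Choosing 15 minutes adds up to 15 − 5 = 10 monitored minutes off oxygen per check, ended on desaturation.

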9.6.5. Physical Examination

To evaluate the subject's eligibility, a physical examination (including height and [recent] body weight measurement, if not already available and if practically feasible) will be performed at screening and at the Final Study Visit/Safety Follow-up Visit (Day 28 or Day 33). In addition, a symptom-directed physical examination will be performed at the time points provided in the [TIME AND EVENTS SCHEDULES](#).

A physical examination includes a review of the following systems: head/neck/thyroid; eyes; ears/nose/throat; respiratory; cardiovascular; lymph nodes; abdomen; skin; musculoskeletal; and neurological. Breast, anorectal, and genital examinations will be performed when medically indicated.

To obtain the actual body weight, subjects must be weighed lightly clothed. The height should be measured barefoot.

Any clinically relevant changes occurring during the study must be recorded in the Adverse Event section of the eCRF.

9.6.6. Specific Toxicities

Diarrhea

Loperamide can be administered.

AST and ALT Elevation

Subjects should be followed until resolution (return to baseline). A subject's study treatment must be discontinued if the subject experiences specific hepatic-related laboratory abnormalities (refer to [Section 10.2](#)).

Clinical Hepatitis

Subjects taking the study drugs should be monitored for the development of signs and symptoms of hepatitis, which include fatigue, malaise, anorexia, nausea, dark urine and clay-colored stools,

bilirubinuria, jaundice, liver tenderness, or hepatomegaly, with or without initially abnormal serum transaminase levels.

Subjects with these signs and symptoms must seek medical attention immediately and have hepatic parameters assessed. Relevant markers of viral hepatitis should also be assessed.

Subjects reporting AST/ALT elevations or clinical hepatitis should be followed until resolution of the AE or toxicity and necessary standard management should be undertaken.

9.7. Biomarker Evaluations

Samples for biomarker analysis will only be obtained and used if not restricted by local regulations. At the time points specified in the [TIME AND EVENTS SCHEDULES](#), a blood sample will be collected for exploratory analyses of biomarkers (host RNA). In addition, leftovers from MT nasal swabs or blood samples may be used for other biomarker analyses (eg, proteins including cytokines).

Samples can only be used for research related to safety, PK, and efficacy of the influenza treatment, or influenza disease. They may also be used to develop tests/assays related to influenza treatment, or influenza disease.

Analyses of biomarkers may be conducted at the sponsor's discretion and may be reported separately from this study.

